## **6.7 Storage**

Investigational product must be stored in the pharmacy as follows: Store at 2-8°C; excursions permitted between 1°C and 15°C. Protect from moisture. Keep bottles tightly closed in a dry place. Do not subdivide and repackage. Do not remove desiccant from the container. Excursions in temperature during storage should be reported by the site. These will be reviewed to determine if the excursion is allowable and the investigational product can be used.

Once the induction seal has been broken, do not return product to the refrigerator but continue to protect agent from moisture. Once the induction seal has been broken, maintain study agent at room temperature (64-79°F or 18-26°C). Keep bottles tightly closed in a dry place.

## **6.8 Pre-Registration and Registration/Randomization**

### **6.8.1 Pre-Registration**

6.8.1.1 To pre-register a participant, send the completed Pre-Registration Eligibility Checklist, to the CPN Registration Office (Email: [[contact]](mailto:[contact]); [contact]) between 8:00 a.m. and 4:30 p.m. Central time, Monday through Friday.

The CPN Registration Office will enter the information into the CPN-hosted database. A unique participant identification number (PID) will be assigned.

6.8.1.2 At the time of pre-registration, the following will be verified:

- CIRB protocol approval and CIRB approval for the registering institution
- Participant eligibility (including existence of a signed informed consent document)
- Existence of a signed authorization for use and disclosure of protected health information (USA Institutions only).
- Study agent is available, and Drug Shipment Authorization has been granted to the registering site.

6.8.1.3 The following also will be recorded:

- Participant has/has not given permission to collect specimens and has/has not agreed that specimen samples and related information may be used for the laboratory studies described in this protocol.
- Participant has/has not given permission for the study doctor, or their representative, to contact him/her or his/her physician to learn about the results of these studies.
- Participant has/has not given permission for their alcohol and tobacco use information to be used for future health research.
- Participant has/has not given permission for specimens and related information to be kept in a Biobank for use in future health research.

- Participant has/has not given permission for specimens and related information to be sent to researchers at outside institutions.
- Participant has/has not given permission to his/her doctor, or their representative, to contact them to see if they wish to participate in other research in the future.

6.8.1.6 Registration Office personnel will automatically register participants separately to the translational components of the study (See Section 13).

## 6.8.2 Registration/Randomization

6.8.2.1 To register a participant, send the completed Registration Eligibility Checklist, to the CPN Registration Office (Email: [[contact]](mailto:[contact]); [contact]) between 8:00 a.m. and 4:30 p.m. Central time, Monday through Friday.

The CPN Registration Office will enter the information into the CPN-hosted database. For randomization details, see Section 13.2.

6.8.2.2 Baseline (screening) and on-study evaluations must be completed within the guidelines specified on the Schedule of Events (See Section 7.1).

6.8.2.3 All baseline symptoms must be documented and graded.

6.8.2.4 Intervention cannot begin prior to registration and must begin  $\leq 14$  days from registration.

6.8.2.5 Intervention on this protocol must commence at a CPN institution under the supervision of a CPN clinician.

6.8.2.6 Stratification Factors: None

## 6.9 Blinding and Unblinding Methods

Pre-registered participants will be assigned a unique subject number, e.g., an 8-character identification number, e.g. CPN00001. Participants will be randomized at registration on Day 1 to receive active intervention or placebo after they have satisfied the inclusion/exclusion criteria. For each participant, the sequence assignment will be determined according to a prepared randomization schedule at the time of registration/randomization. The assigned study agent bottle number generated for each randomized participant will be sent to the Thomas Jefferson University personnel. Pharmacy personnel will not be blinded to intervention arm assignment.

The study will be double-blinded until after specimen analysis to ensure that the participants, investigators, and clinic staff are unaware of the dosing assignment and to minimize potential for bias in study assessments or in reporting of AEs.

There are two distinct situations in which it will be deemed appropriate to break the randomization assignment for participants enrolled onto this current trial:

- In the event of an *emergency* for an individual participant.
- Serious Adverse Event (SAE) that fulfills the criteria for expedited reporting to the FDA.

In these situations, Participating Organization personnel may assume the participant is on active agent and call the CPN Registration Office within one business day to receive unblinding information. The study name/number, participant identifier, and participant initials will be required to break the randomization code. Thomas Jefferson University personnel are responsible for notifying the medical monitor at DCP, NCI of the unblinding event.

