## 6.6 Packaging and Labeling

Investigational product will be supplied in the form of gelatin capsules. For the intervention period, participants will be assigned dolcanatide (3 capsules each containing 9 mg dolcanatide, daily x 7 days) or identically-appearing placebo (3 capsules daily x 7 days), according to the intervention arm assignment. The placebo capsule will be identical in appearance and will contain methyl cellulose.

All investigational products will be supplied in bottles containing 24 capsules each, and will be labeled with the following content: protocol number, storage information, investigational use language (“Caution: New Drug--Limited by Federal Law to Investigational Use. Keep Out of Reach of Children”), and instructions to take per protocol. The label will also include a tear-off component, to be removed by the unblinded site pharmacist prior to dispensing. The tear-off label component will identify the contents of the bottle as being active agent or placebo. This tear-off label will be maintained in the secure pharmacy records until requested by the study statistical team or if unblinding is required in an emergency situation. The site investigators, study coordinators, and study participants should remain blinded to the intervention assignment.

All study agent will be received and stored at the Thomas Jefferson University Hospital (TJUH) Investigational Drug Service Pharmacy (IDS). Initial dispensing for individual properly randomized participants will be done by TJUH IDS pharmacists. Study agent will be dispensed to designated Research Nurses. Immediately before dispensing investigational product to a participant, the designated Research Nurses will write the participant’s initials, participant identification number, and dispensing date on the label. After initial Day 1 dosing, blinded bottles will be stored in the CRU storage pharmacy until end of study and all monitoring on drug has been completed. All dosing of participants will occur in the CRU. Accurate chain of custody logs and dosing records will be maintained.

Dolcanatide 9 mg or Placebo	24 Capsules
Protocol MAY2017-09-01	
Bottle # _____	
Participant ID # _____	
Dispensing Date _____	
Take per protocol	
Store refrigerated 36°F - 46°F (2 °C – 8 °C). Keep product in the original container. Do not subdivide or repackage. Protect from moisture. Do not remove desiccant from the container. Keep bottles tightly closed in a dry place. Keep Out of Reach of Children.	

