#### **7.5 Post-intervention Follow-up Period**

On Day 21 (+/- 3 days), approximately 14 days after the last dolcanatide or placebo dosing, participants will come to the CRU at TJU for a post-intervention visit. Participants will undergo physical exam, vital signs (weight, heart rate, blood pressure and temperature), laboratory safety (blood and urine) as previously described, AE and concomitant medication monitoring, complete the alcohol and tobacco use follow up assessments (Appendix D), and complete the Was It Worth It (WIWI) questionnaire (Appendix C). The AE monitoring will include querying whether participants experienced any changes in bowel habits while on study agent and, if so, the duration of these changes and how long it required to return to normal. Similarly, the interview will include querying whether participants experienced any side effects that would prevent them from taking the study agent for long periods.

Participants will receive a follow-up telephone call 30 days (+/- 7 days) after the end of post-intervention to determine the status of any ongoing AEs reported at the Day 21 evaluation. Follow up will be performed via telephone or in person as deemed appropriate by the lead investigator at the participating site.

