### **10.2 Collection and Handling Procedures**

- Eight mucosa biopsies will be collected from the rectum (at or just above the inferior valve of Houston) pre-intervention and post-intervention (Day 7, after administration of dolcanatide or placebo for 7 days).
- Five biopsies will be flash-frozen in liquid nitrogen individually in a screw cap vial and provided a sample-specific ID. Among the 5 biopsies, 2 of them will be evaluated for cGMP concentration. Frozen tissues will be transferred and stored at -80°C in [name] laboratory. In addition, 3 biopsies will be flattened immediately and fixed in 10% formalin within 2 min of collection in pre-labeled cassettes with tracking information provided, for future Ki67 immunohistochemistry analysis, if necessary.
- After formalin fixation overnight, samples will be transferred to 70% ethanol and sent to the Pathology Department for routine tissue processing. Processed tissue will be transferred to [name] laboratory for biomarker studies.
- All specimens from the each biopsy will be put into pre-labeled containers separated for analysis.
- Containers will be labeled with study number, registration number, date/time of collection, anatomical location and biopsy number. For example, 000-D7-Rec-1.
- Specimen manifest will be sent by email to the Biospecimens Resource Manager at the time of shipment.

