**To confirm the safety and tolerability of dolcanatide:** Summary statistics and frequency tables will be used to describe the data in an exploratory fashion. All adverse events will be summarized by treatment arm and compared between arms using the Fisher's Exact test. All eligible participants initiating study intervention will be considered evaluable for this endpoint.

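### Section 6.9 lets the study blind end once specimens are analysed, which can precede the last participants' Day 21 and Day 51 safety contacts (minor)

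*Combined protocol and SAP*

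**What the plan says.** Section 6.9 sets the end of the blind: "The study will be double-blinded until after specimen analysis to ensure that the participants, investigators, and clinic staff are unaware of the dosing assignment". The sentence then adds a second aim, "to minimize potential for bias in study assessments or in reporting of AEs". On individual code breaks the section says: "There are two distinct situations in which it will be deemed appropriate to break the randomization assignment for participants enrolled onto this current trial". The two situations are an emergency and an SAE that meets the criteria for expedited FDA reporting.

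Section 6.6 also covers blinding: "The site investigators, study coordinators, and study participants should remain blinded to the intervention assignment". It gives no end point. On the label that identifies the bottle contents it says: "This tear-off label will be maintained in the secure pharmacy records until requested by the study statistical team", or until emergency unblinding is needed. No date or milestone is attached to the statisticians' request.

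Safety data continue after the last biopsy. In the Schedule of Events (section 7.1, footnotes 7 and 9), Day 7 AEs are assessed before the dose and before sigmoidoscopy. The next scheduled AE recording is Day 21. Section 7.5 describes that visit: "The AE monitoring will include querying whether participants experienced any changes in bowel habits while on study agent". It also covers how long such changes lasted and whether side effects would prevent long-term use. AEs unresolved at Day 21 are reviewed at about Day 51.

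Safety and tolerability against placebo is a secondary objective (section 1.2). Section 13.5 says: "All adverse events will be summarized by treatment arm and compared between arms using the Fisher's Exact test". Relatedness is a five-level judgement (section 11.1.4), and section 13.7 uses it to define toxicities.

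**The concern.** The event that ends the blind is tied to the primary endpoint, whose specimens are complete at Day 7. One purpose given for the blind is unbiased AE reporting, which runs past that point. Day 21 is the first scheduled AE recording after the final dose and the second biopsy. Its questions are subjective and ask for recall of about two weeks. If the code were open by then, knowledge of the arm could colour what a participant reports and how the investigator attributes it.

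Sections 6.6 and 6.9 also do not match. One keeps site staff and participants blinded with no end point, and the other names an end point earlier than the last safety contact. A reader cannot tell which governs. At stake is the credibility of the late AE data for the participants enrolled last.

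**Working it through.** **Inputs.** 24 participants (section 13.1); 4 randomised per month and a maximum of 7 months to determine the primary endpoint (section 13.3); last biopsy Day 7, AE visit Day 21 (± 3 days), contact at about Day 51 (sections 7.1 and 7.5). The assay lag is not stated, so it is varied. Even spacing and 30.44 days per month are assumed.

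**The plan's own timeline.** 24 / 4 = 6 months of accrual. The last Day 1 falls at 5.75 to 6.0 months, depending on whether the first participant starts at month 0 or one interval later. Adding 6 days puts the last Day 7 biopsy at 5.9 to 6.2 months. The 7-month maximum is consistent with this.

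**Participants still in follow-up.** The spacing is 30.44 / 4 = 7.61 days. If assays finish *L* days after the last biopsy, a participant enrolled *k* places before the last still awaits Day 21 if 7.61*k* < 14 − *L*, and Day 51 if 7.61*k* < 44 − *L*. Counting from *k* = 0:

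| Lag *L* (days, assumed) | Awaiting Day 21 | Awaiting Day 51 |
|---|---|---|
| 0 | 2 of 24 | 6 of 24 |
| 7 | 1 | 5 |
| 14 | 0 | 4 |
| 21 | 0 | 4 |
| 30 | 0 | 2 |
| 44 | 0 | 0 |

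These use nominal days. At the late edge of the windows (+3 and +7 days), the zero-lag limits become 14 + 3 = 17 and 44 + 7 = 51 days. Then 17 / 7.61 = 2.2 and 51 / 7.61 = 6.7, so each top count rises by one, to 3 and 7.

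**At the 7-month limit.** The primary endpoint is a between-arm comparison, so, read literally, completing it needs the codes. At 7 months the last participant is at about study Day 31 to 39. No Day 21 visit is outstanding. Nominal Day 51 is outstanding for 2 to 3 participants (3 to 4 with the +7 window).

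**After the fix.** The last nominal Day 51 is 44 days after the last biopsy, at about 7.4 to 7.6 months. With the +7 window it is 51 days after, at about 7.6 to 7.9 months. That is 44 / 7 = 6.3 to 51 / 7 = 7.3 weeks after the last biopsy, within the approximately 1.0 year stated in section 13.3. Sample size, power and alpha do not change.

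**The case against.** A reader might infer that the whole safety comparison could be made unblinded. The documents do not support that. Section 6.9 describes a study-level blind and lists only two reasons to break an individual code, so only the last few enrolled are exposed. AEs are also recorded before each daily supervised dose and before the Day 7 sigmoidoscopy, so much of the on-treatment diarrhoea and cramping would be captured under the blind. Day 51 mainly follows events already recorded.

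A reader might also infer that the stopping rule in section 13.7.1 is compromised. Its suspension provision acts on accrual, and once every Day 7 specimen has been analysed there is no accrual left to suspend.

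A third tempting step is that one re-attributed event moves an arm's rate by 1/12 = 8.3 percentage points in the between-arm test. The Fisher comparison in section 13.5 is of all AEs, not of related ones, so re-attribution does not enter it. Relatedness matters for the toxicity summaries in section 13.7, which are descriptive.

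Further points count in the plan's favour. The wording in 6.9 sets an earliest time and does not order unblinding then. The statisticians who may request labels do not interview participants. Section 6.6 keeps site staff and participants blinded. The assay takes time (section 9.1 includes an overnight digestion), so zero lag is an extreme. The consortium's master data management and safety monitoring plans, which were not supplied, may contain lock procedures.

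All of this limits the size of the problem. It does not close the gap: no supplied text ties the end of the blind to the last safety contact, and 6.6 and 6.9 remain unreconciled.

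**Conclusion.** The point holds as a minor one. As written, the code may be opened before the last-enrolled participants finish safety follow-up, contrary to the stated aim of protecting AE reporting. At nominal visit days the exposure is 0 to 2 of 24 for Day 21, and only if assays and code release are complete within about two weeks of the last biopsy (about 17 days with the visit window). For Day 51 it is 0 to 6 of 24, or 2 to 3 at the stated 7-month limit.

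These counts assume even accrual at 4 per month and an assay lag that the documents do not give. The Day 51 counts are ceilings, because that contact concerns only AEs unresolved at Day 21. What could be affected is late AE reporting and descriptive attribution. The primary endpoint and the accrual suspension rule are not affected, and re-attribution cannot alter the Fisher comparison.

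**What to change.** In section 6.9, state that participants, investigators, clinic staff and laboratory staff stay blinded until specimen analysis is complete, the last participant's Day 21 visit and any Day 51 AE contact are done, and the database is locked. In section 6.6, give the blinding statement the same end point and make routine release of the tear-off labels to the statistical team conditional on that lock. Leave emergency unblinding as it is.

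The Day 51 window should be reconciled at the same time, since it determines when the last contact can fall: the schedule header and section 7.5 give ± 7 days, and footnote 10 gives ± 3 days.

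The cost is a few sentences and a wait of at most about 6 to 7 weeks after the last Day 7 biopsy. The added delay is shorter to the extent that the assays take time anyway.

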#### **6.10 Agent Destruction/Disposal**

At the completion of investigation and after the close-out visit by the CPN Compliance Coordinator, all unused study agent will be returned to Synergy Pharmaceuticals, or their designee.

## 7. CLINICAL EVALUATIONS AND PROCEDURES

### 7.1 Schedule of Events

Study Day	Pre-Registration and Screening 1 ≤ 30days prior to Registration	Baseline		On-Study Procedures				Post-Intervention	
		Screening 2	Registration/ Randomization	Day 1	Days 2-5	Day 6	Day 7	Day 21 (+/- 3 days)	Day 51 (+/- 7 days)
Informed consent	X								
Assess Eligibility	X		X						
Medical History	X								
Tobacco and Alcohol Use Assessments	X							X	
Physical Exam	X						X	X	
Baseline Symptoms	X								
Vital Signs	X	X					X 	X 	
Safety Blood tests	X						X	X	
Pregnancy Test (urine or serum) 	X		X 						
ECG	X								
Urinalysis and Urine Drug Screen 	X						X	X	
Discharge from CRU		X 					X 		
Sigmoidoscopy and Biopsy		X					X		
Light Breakfast 		X		X	X	X			
Light meal		X					X		
Dose Administration				X	X	X	X		
Adverse Event Recording		X 	X 	X 	X 	X 	X 	X	X 
Concomitant Medications	X	X	X	X	X	X	X	X 	X 
WIWI Questionnaire								X 	
Follow-up Phone Call									X

- Heart rate, height, weight, and blood pressure. Height will not be measured at Day 7 or Day 21.
- For women of childbearing potential only. Negative pregnancy test (serum or urine) must be documented ≤7 days prior to registration.

3. Repeat pregnancy test, only if applicable and not performed  $\leq 7$  days prior to registration.
4. May be repeated at any time at the discretion of the investigator.
5. Discharge after full recovery from flexible sigmoidoscopy.
6. The breakfast will be provided by staff from the CRU.
7. Adverse events will be assessed prior to flexible sigmoidoscopy.
8. Adverse events will be assessed at this time point only for individuals found to be ineligible for randomization.
9. Adverse events will be assessed prior to administration of study agent.
10. If any reported AEs are not resolved at the time of the Day 21 follow up, another contact will be made at Day 51 (+/- 3 days) to review AEs. SAEs at least possibly related to the use of study agent will be followed until resolved. Concomitant medications need only be reported if AEs are reported.
11. Was It Worth It (WIWI) Questionnaire and repeat Alcohol/Tobacco Assessments at Day 21 or early termination.

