### **3. SUMMARY OF STUDY PLAN**

Healthy volunteers 18-65 years old, without personal or family (first degree relative) history of colorectal neoplasia, inflammatory bowel disease or other recent ( $\leq 3$  months prior to day 0) or ongoing disease states producing acute or chronic diarrhea will be pre-registered in the study. Pre-registered participants will receive a flexible sigmoidoscopy procedure before receiving the test drug (See Section 7.6 for details concerning type of pre-procedure bowel preparation).

Those who have satisfactory rectal preparation, effective forward progress of the scope to at least 25 cm, and no significant intestinal pathology visualized will be formally registered (accrued). During the pre- and post-intervention sigmoidoscopies, 8 biopsies from the rectum will be taken at each time point. Registered participants will receive dolcanatide at a dose of 27 mg daily or placebo daily for 7 days. Post intervention physical exams, laboratory safety examination, AE monitoring, and questionnaire data will be performed or collected 14 days (+/- 3 days) after the last dose of the assigned study agent.

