## **5.7 Adherence/Compliance**

Dolcanatide will be administered under direct supervision of the Clinical Research Unit (CRU) staff at Thomas Jefferson University every morning between 07:00 and 09:00.

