## **7.2 Baseline Testing/Prestudy Evaluation**

### **Screening 1**

Within 30 days prior to registration, participants will undergo a screening visit. Informed consent will be obtained. Potential participants will be pre-registered (See Section 6.8.1). They will undergo medical history, tobacco and alcohol use assessments, physical exam, vital signs (height, weight, heart rate, blood pressure, and ECOG performance status), electrocardiogram, and laboratory safety evaluations. Laboratory safety evaluation will include albumin, total bilirubin, calcium, bicarbonate, chloride, creatinine, glucose, alkaline phosphatase, potassium, total protein, sodium, AST/SGOT, ALT/SGPT, and BUN; CBC with differential; PTT and PT/INR; urinalysis; urine drug screen; and FSH (for post-menopausal women only). They will be asked about baseline symptoms and concomitant medications. Women of childbearing potential must document a negative pregnancy test (urine)  $\leq 7$  days prior to Registration.

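### The pregnancy test is tied to registration and not to first dose, so the written rules permit a test up to 21 days old when dosing starts

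*Combined protocol and SAP*

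**What the plan says.** Section 7.1, footnote 2, sets the rule: "Negative pregnancy test (serum or urine) must be documented ≤7 days prior to registration". Footnote 3 governs the one repeat slot, in the Registration/Randomization column: "Repeat pregnancy test, only if applicable and not performed" within that same 7-day window. The Screening 1 text in section 7.2 begins "Women of childbearing potential must document a negative pregnancy test (urine" and again counts the 7 days back from registration.

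The Schedule prints Registration/Randomization and Day 1 as separate columns and gives no interval between them. Dosing starts in the Day 1 column, where the pregnancy-test row is empty. The footnote allowing repeats at the investigator's discretion belongs to the urinalysis and drug-screen row, not to the pregnancy-test row.

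Two sets of text bear on the gap between registration and first dose:

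- Sections 6.9 and 13.2 both place registration on Day 1.
- Section 6.8.2.4 states "Intervention cannot begin prior to registration and must begin" no more than 14 days after it. This is the only numeric limit on the gap in the document.

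**The concern.** Section 6.2 says that effects on the embryo or fetus are unknown and that pregnant women should not receive the drug. Section 4.2.13 makes pregnancy an exclusion. The test is the objective check behind that exclusion, and what it protects against is exposure, which begins with the first dose. A window counted back from registration protects equally well only if registration and first dose are close together. The plan has text that puts them on one day and a clause that lets them lie two weeks apart, and the test rule does not respond to the difference. If the start were delayed, a woman who conceived after her test could be dosed without any rule having been broken.

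**Working it through.** The plan states no test age at first dose, so there is no figure of its own to reproduce. The check is day arithmetic.

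**Inputs**

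- Longest interval from test to registration: 7 days (section 7.1, footnotes 2 and 3; section 7.2).
- Gap from registration to first dose: 0 days if both are on Day 1 (sections 6.9 and 13.2); at most 14 days under section 6.8.2.4.
- Repeat test after registration: none scheduled (section 7.1).

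**Formula**

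Maximum test age at first dose = longest interval from test to registration + gap from registration to first dose.

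| Reading | Calculation | Maximum test age |
|---|---|---|
| Registration and first dose both on Day 1 | 7 + 0 | 7 days |
| Full allowance in 6.8.2.4 used | 7 + 14 | 21 days |
| Test required within 7 days before first dose (proposed) | 7, whatever the gap | 7 days |

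The second row exceeds a 7-day window anchored to first dose by 21 - 7 = 14 days. Footnote 3 does not close that gap: it looks only at whether the test was current at registration, which it was.

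**How many women**

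The planned enrollment table in section 13.3 has 8 + 1 = 9 women of 24. With 12 of 24 on active drug, about 9 × 12/24 = 4.5 of them would receive dolcanatide. Section 4.5 gives the site's historical share of women as about 10%; on that basis, 0.10 × 24 = 2.4 women, about 1.2 on dolcanatide. The number of childbearing potential is not stated. Entry runs to age 65, so it is likely to be lower than either total.

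**The case against.** The strongest answer is that the schedule already delivers what is asked. With registration and first dose both on Day 1, a test within 7 days of one is within 7 days of the other, and footnote 3 requires a repeat if the window has lapsed. Moreover, section 5.1 puts the baseline biopsies on Day -1 and section 3 says that those with "no significant intestinal pathology visualized will be formally registered (accrued", so registration follows that procedure. If the numbering is held to strictly, a 14-day gap cannot arise. This stands as a description of the intended conduct. It does not remove the point, because the permission in 6.8.2.4 is written as the start-window rule and nothing subordinates it to the other sections. The day numbering is also not firm enough to settle the matter: section 7.6 puts the first sigmoidoscopy on day 1, and the Screening 2 column in 7.1 carries no day number.

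Three stronger readings are tempting, and the documents do not support them.

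- A reader might infer that 6.8.2.4 contradicts 6.9 and 13.2. It does not. A 14-day ceiling is satisfied by a gap of zero, so all three can be obeyed together. The allowance is unreconciled with the Day 1 text and has no use if that text is followed.
- A reader might infer that women would normally be registered right after the baseline procedure and dosed a day or more later, so that even the intended schedule overruns 7 days. No section places registration on Day -1. The day 0 in section 3 appears only in an eligibility look-back for diarrheal disease.
- A reader might infer that same-day registration is unworkable, because the registration office works "between 8:00 a.m. and 4:30 p.m. Central time, Monday through Friday" and dosing is "every morning between 07:00 and 09:00". That depends on the site's time zone and on weekend starts, neither of which the documents state.

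It is also fair to say that practical risk is low. Section 4.1.4 requires contraception, dosing lasts 7 days, and section 2.2.2 reports minimal systemic exposure.

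**Conclusion.** The point holds as a minor participant-safety improvement. The test is anchored to the wrong event. Its age at first dose is at most 7 days if Day 1 registration is followed, and up to 21 days if the full allowance in 6.8.2.4 is used. The 21 days is an outer limit on what the written rules permit; nothing in the documents suggests that it is planned or likely. It rests on reading 6.8.2.4 literally and on there being no further test rule elsewhere. The consent pages are not in the copy reviewed, so any timing given there could not be checked. Sample size, type I error, power and the primary analysis are unaffected.

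**What to change.** - In section 7.1, footnotes 2 and 3, and in section 7.2, require for women of childbearing potential a negative test within 7 days before the first dose, repeated before Day 1 dosing if that window has lapsed. Mark the conditional repeat in the Day 1 column.
- Reconcile 6.8.2.4 with 6.9 and 13.2. Either drop the 14-day allowance, or, if a delayed start is wanted, say so and stop describing registration as a Day 1 event.
- While those lines are open, make the specimen type agree: 7.1 accepts serum or urine, and 7.2 mentions urine only.

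Anchoring to first dose caps test age at 7 days however the start window is resolved. The cost is a wording change in a few places and at most a few repeat urine tests, given at a visit the participant already attends.
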